4. MATERIALS AND METHODS

4.1 PATIENTS

Approximately 7 sites will participate to enroll approximately 120 patients with a diagnosis of COPD across two cohorts. Approximately 100 patients with COPD (GOLD 2–4) will be randomized to Cohort A; patients with chronic bronchitis ($n \leq 60$) and without chronic bronchitis ($n \geq 40$) will be randomized across treatment arms. Approximately 20 patients (GOLD 1) will be enrolled in the Cohort B substudy.

4.1.1 Inclusion Criteria

Patients must meet the following criteria for study entry:

- Age ≥ 40 years at time of signing Informed Consent Form
- Ability to comply with the study protocol, in the investigator's judgment
- Signed Informed Consent Form (signed before any study procedures are performed)
- Current or former smokers with ≥ 10 pack years
- mMRC dyspnea score ≥ 1
- Post-bronchodilator FEV₁/forced vital capacity (FVC) <0.70 at screening (Visit 1) or randomization (Visit 2)
- For patients enrolled in Cohort A: GOLD Stage 2–4 COPD with a history of ≥ 2 moderate/severe exacerbations within a 12-month period in the 24 months prior to screening
- For patients enrolled in Cohort B: GOLD Stage 1 COPD with a history of ≥ 1 moderate/severe exacerbations within a 12-month period in the 24 months prior to screening
- Receiving SOC background drug therapy as per GOLD or British Thoracic Society (BTS) guidance for COPD for 12 weeks prior to screening (Visit 1)

- On an eligible bronchodilator medication (LABA and/or LAMA) \pm ICS therapy for ≥ 12 weeks prior to screening (Visit 1)
- Chest X-ray or CT scan within 6 months prior to screening (Visit 1), or during the screening period (prior to randomization [Visit 2]), that confirms the absence of clinically significant lung disease besides COPD
- For women of childbearing potential: agreement to remain abstinent (refrain from heterosexual intercourse) or use adequate contraception during the study period (all patients) and for 28 days after the final dose of azithromycin (patients enrolled in Cohort A receiving azithromycin)

A woman is considered to be of childbearing potential if she is postmenarchal, has not reached a postmenopausal state (≥ 12 continuous months of amenorrhea with no identified cause other than menopause), and is not permanently infertile due to surgery (i.e., removal of ovaries, fallopian tubes, and/or uterus) or another cause as determined by the investigator (e.g., Müllerian agenesis). The definition of childbearing potential may be adapted for alignment with local guidelines or regulations.

The following are examples of adequate contraceptive methods: bilateral tubal ligation; male sterilization; hormonal contraceptives; hormone-releasing intrauterine devices; copper intrauterine devices; male or female condom with or without spermicide; and cap, diaphragm, or sponge with spermicide.

The reliability of sexual abstinence should be evaluated in relation to the duration of the clinical trial and the preferred and usual lifestyle of the patient. Periodic abstinence (e.g., calendar, ovulation, symptothermal, or postovulation methods) and withdrawal are not adequate methods of contraception.

If required per local guidelines or regulations, locally recognized adequate methods of contraception and information about the reliability of abstinence will be described in the local Informed Consent Form.

4.1.2 Exclusion Criteria

Patients who meet any of the following criteria will be excluded from study entry:

- History of allergy or hypersensitivity to azithromycin
- Significant known respiratory disorders other than COPD that, in the view of the investigator, will affect the trial
- A COPD exacerbation and/or pneumonia within the 4 weeks prior to screening (Visit 1)
- FEV₁ percent predicted less than 25%
- Pregnant or breastfeeding, or intending to become pregnant during the study period (all patients) or within 28 days after the final dose of azithromycin (patients enrolled in Cohort A receiving azithromycin)

Women of childbearing potential must have a negative serum pregnancy test result at screening.

- Participation in an interventional clinical trial within 4 weeks of screening (Visit 1) or receipt of any investigational medicinal product (IMP) within 30 days or 5 half-lives, whichever is longer
- Use of systemic corticosteroids within 4 weeks (oral or IV) or 12 weeks (intramuscular [IM]) prior to screening
- Active tuberculosis requiring treatment within 12 months prior to Visit 1

Patients who have completed treatment for tuberculosis at least 12 months prior to Visit 1 and have no evidence of recurrent disease are permitted.
- Receiving treatment considered to be palliative (life expectancy <12 months)
- Myocardial infarction, unstable angina, or stroke within 12 months prior to screening (Visit 1)
- Clinically significant ECG changes, which in the opinion of investigator warrants further investigation or with a QTc interval > 450 ms
- History of congenital or documented QT prolongation
- Currently receiving treatment with other active substance at doses known to prolong QT interval such as antiarrhythmic of Classes Ia and III, cisapride, and terfenadine
- Electrolyte disturbance (e.g., clinically significant hypokalemia or hypomagnesemia)
- Clinically relevant bradycardia, cardiac arrhythmia, or severe cardiac insufficiency
- History of myasthenia gravis
 - For patients in Cohort A: Known *significant hearing impairment as indicated by a score of ≥ 26 on the Hearing Handicap Inventory in the Elderly—Screening Questionnaire (HHIE-S) or as determined by the investigator*
- Impaired hepatic function
- Severe renal insufficiency (estimated glomerular filtration rate [eGFR] <10 mL/min)
- Concomitant use of ergot derivatives
- Bloodborne infection (e.g., HIV, hepatitis B or C)
- History of *Clostridium difficile* (*C. difficile*) diarrhea
- Ventricular cardiac arrhythmia in the past 30 days
- Claustrophobia, inner ear implants, aneurysm or other surgical clips, metal foreign bodies in eye, pacemaker or other contraindication to MRI scanning

Patients with any implanted device that cannot be verified as MRI compliant will be excluded.
- Unable to fit into ^{129}Xe vest coil used for MRI
- Deemed unlikely to be able to comply with instructions during imaging
- Evidence, in the opinion of the investigator, of alcohol, drug, or solvent abuse within the prior 12 months

- Medical or psychological conditions which, in the opinion of the investigator, might create undue risk to the patient or interfere with the patient's ability to comply with the protocol requirements
- Diagnosis of malignancy within 5 years of Visit 1 (except for excised localized non-melanoma skin cancer in remission)

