4.5.1 Informed Consent Forms and Screening Log

Written informed consent for participation in the study must be obtained before performing any study-related procedures (including screening evaluations). Informed Consent Forms for enrolled patients and for patients who are not subsequently enrolled will be maintained at the study site.

All screening evaluations must be completed and reviewed to confirm that patients meet all eligibility criteria before enrollment. The investigator will maintain a screening log to record details of all patients screened and to confirm eligibility or record reasons for screening failure, as applicable.

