4.5.2 Medical History, Baseline Conditions, Concomitant Medications, and Demographic Data

Medical history, including clinically significant diseases, surgeries, cancer history (including prior cancer therapies and procedures), reproductive status, medication allergies, smoking history, and use of alcohol and drugs of abuse will be recorded at screening. In particular, sites should record whether the patient has any history of anaphylaxis, cancer, cardiovascular disease, eosinophilic disease, inflammatory or autoimmune disease, and surgeries with metal implants. Any history of smoking should be entered on the Tobacco Use History eCRF.

Demographic data will include age (date of birth), sex, and self-reported race/ethnicity.

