5.1.2.1 Hypersensitivity

As with erythromycin and other macrolides, serious allergic reactions including angioneurotic edema and anaphylaxis (rarely fatal), Acute Generalized Exanthematous Pustulosis (AGEP), and Drug Reaction with Eosinophilia and Systemic Symptoms (DRESS) have been reported. Some of these reactions with azithromycin have resulted in recurrent symptoms and required a longer period of observation and treatment.

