5.1.2.9 Hypersensitivity: Rash, Pruritus, Tongue, or Facial Swelling

The only contraindication listed in the E.U. Summary of Product Characteristics for azithromycin is giving it to patients with known hypersensitivity to macrolide antibiotics.

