5.6 ADVERSE EVENTS THAT OCCUR AFTER THE ADVERSE EVENT REPORTING PERIOD

The Sponsor should be notified if the investigator becomes aware of any serious adverse event that occurs after the end of the adverse event reporting period (defined as 28 days after the final dose of study drug), if the event is believed to be related to prior study treatment. These events should be reported through use of the Adverse Event

¹²⁹Xe MRI—Genentech, Inc.

66/Protocol GE42063, Version 5

eCRF. However, if the EDC system is not available, the investigator should report these events directly to the Sponsor or its designee, either by faxing or by scanning and emailing the paper Clinical Trial Serious Adverse Event/Adverse Event of Special Interest Reporting Form using the fax number or email address provided to investigators.

5.7 EXPEDITED REPORTING TO HEALTH AUTHORITIES, INVESTIGATORS, INSTITUTIONAL REVIEW BOARDS, AND ETHICS COMMITTEES

The Sponsor will promptly evaluate all serious adverse events and adverse events of special interest against cumulative product experience to identify and expeditiously communicate possible new safety findings to investigators, IRBs, ECs, and applicable health authorities based on applicable legislation.

To determine reporting requirements for single adverse event cases, the Sponsor will assess the expectedness of these events through use of the reference safety information in the documents listed below:

Drug	Document
Azithromycin	Single drug covered by prescribing information: Azithromycin E.U. Summary of Product Characteristics
¹²⁹ Xe MRI	Drug device combination covered by combination Investigator's Brochure: HP ¹²⁹ Xe and MRI Investigator's Brochure

HP = hyperpolarized; MRI = magnetic resonance imaging.

The Sponsor will compare the severity of each event and the cumulative event frequency reported for the study with the severity and frequency reported in the applicable reference document.

Reporting requirements will also be based on the investigator's assessment of causality and seriousness, with allowance for upgrading by the Sponsor as needed.

A SMC will monitor the incidence of the above-listed anticipated events during the study. An aggregate report of any clinically relevant imbalances that do not favor the test product will be submitted to health authorities.

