9.2 PROTOCOL DEVIATIONS

The investigator should document and explain any protocol deviations. The investigator should promptly report any deviations that might have an impact on patient safety and data integrity to the Sponsor and to the IRB/EC in accordance with established IRB/EC policies and procedures. The Sponsor will review all protocol deviations and assess whether any represent a serious breach of Good Clinical Practice guidelines and require reporting to health authorities. As per the Sponsor's standard operating procedures, prospective requests to deviate from the protocol, including requests to waive protocol eligibility criteria, are not allowed.

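### The eligibility lists name only azithromycin allergy, although the protocol reports a class-wide macrolide contraindication; keeping other macrolide allergies out of Cohort A depends on investigator judgment

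*Combined protocol and SAP*

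**What the plan says.** The synopsis and Section 4.1.2 carry the same drug-allergy exclusion, "History of allergy or hypersensitivity to azithromycin". It applies to all patients, and neither list names any other drug allergy.

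Section 5.1.2.9 describes the contraindication differently. As the protocol reports it, the E.U. Summary of Product Characteristics lists one contraindication for azithromycin: "giving it to patients with known hypersensitivity to macrolide antibiotics". Section 5.1.2.1 also treats serious allergic reaction as a risk that azithromycin shares with erythromycin and the other macrolides.

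Four further provisions bear on how such a patient would be handled:

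- Section 4.5.2 says that, among other history items, "medication allergies, smoking history, and use of alcohol and drugs of abuse will be recorded at screening". It also asks sites to record any history of anaphylaxis.
- Both exclusion lists contain a general item: "Medical or psychological conditions which, in the opinion of the investigator, might create undue risk to the patient".
- Section 4.5.1 requires an eligibility check: "All screening evaluations must be completed and reviewed to confirm that patients meet all eligibility criteria before enrollment".
- Section 9.2 says that "requests to waive protocol eligibility criteria, are not allowed".

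Under Section 4.2, Cohort A is randomized 1:1 to azithromycin plus standard of care or to standard of care alone. Cohort B receives no azithromycin.

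**The concern.** The entry rule is narrower than the contraindication printed in the same protocol. Azithromycin allergy is an outright exclusion, so the gap concerns one kind of candidate: someone considered for Cohort A who has a known allergy to a different macrolide and none known to azithromycin. The protocol's own safety section places that person in the group for whom the drug is contraindicated, yet no listed criterion says so.

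What is at stake is patient safety and consistency between sites. With about 7 sites, two investigators could read the same erythromycin allergy differently, and both would be acting within the protocol. The estimand, sample size and planned analyses are not involved.

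**Working it through.** The protocol states no figure on this point, so the check is a comparison of texts.

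**Step 1: scope of the exclusion against scope of the contraindication.** The exclusion in the synopsis and 4.1.2 covers one drug. The contraindication reported in 5.1.2.9 covers the macrolide class. The difference between them is allergy to a macrolide other than azithromycin. Neither the rest of the exclusion lists, nor the concomitant-therapy rules in 4.4, nor the discontinuation rules in 4.6.1, nor the schedule of activities in Appendix 1 names that allergy.

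**Step 2: is the narrower wording a stated choice?** Other azithromycin risks in Section 5.1.2 were carried into 4.1.2 as named exclusions:

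- myasthenia gravis (5.1.2.6)
- history of *C. difficile* diarrhea (5.1.2.5)
- impaired hepatic function (5.1.2.2 and 5.1.2.8)
- significant hearing impairment, Cohort A only (5.1.2.7)
- QT prolongation (5.1.2.10)
- concomitant ergot derivatives (5.1.2.3), where the protocol describes the interaction as only theoretical

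The one item that 5.1.2.9 calls a contraindication in the product document is carried over for a single member of the class, and no reason is given. This looks like an omission, though the text cannot settle the intent.

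**Step 3: what happens to the affected candidate as the protocol stands?** The allergy is recorded under 4.5.2. The review under 4.5.1 then checks the candidate against every criterion, including the undue-risk item. If the investigator considers the allergy an undue risk, that criterion is met and the candidate must be excluded. If not, no other criterion stops enrollment on account of the allergy. The outcome turns on that one decision.

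**Step 4: size.** The only figure the documents support is the allocation probability. For each such patient already admitted to Cohort A, P(assigned azithromycin) = 1/(1+1) = 0.5, from the 1:1 ratio in 4.2. This is a chance of exposure given admission, not a chance of a reaction. The documents give no prevalence of allergy to other macrolides, no share that investigators would exclude as an undue risk, and no cross-reactivity rate. The expected number of patients and the expected harm therefore cannot be calculated.

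**The case against.** The strongest reply is that the protocol already has the information and a route to exclusion. Medication allergies and any history of anaphylaxis are recorded before the eligibility review, the contraindication is printed in the safety section, and the undue-risk item is itself a listed exclusion. To enroll such a patient, an investigator would have to see the allergy and decide that a contraindication stated in the protocol creates no undue risk. A careful investigator would probably not do so. The current wording also leaves room to admit a patient who has tolerated azithromycin despite reacting to another macrolide. All of this stands, and it limits the severity. It does not remove the mismatch, because the safeguard still depends on opinion and the protocol gives no reason for the narrower rule.

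Several stronger readings are tempting but not supported:

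- *A named criterion could not be waived, whereas the undue-risk item could.* Section 9.2 bars waivers of eligibility criteria without distinguishing between kinds. Once the undue-risk item is met, exclusion is just as binding.
- *The eligibility review cannot catch this allergy.* It can, because the undue-risk item is among the criteria reviewed. What is missing is an explicit label.
- *Only a named criterion can prevent first exposure.* The undue-risk item also acts at entry. Section 4.6.1 in addition requires treatment to stop for any condition that the investigator or Sponsor decides may endanger the patient, and that rule is not tied to an adverse event having occurred.
- *The toxicity grading of allergic reactions makes the gap worse.* Grading and stopping rules concern anyone on azithromycin. They do not bear on who is eligible.
- *Self-administration of the first dose means unsupervised dosing.* Section 3.1 places the dose after all scheduled assessments, and 4.3.2.1 has the tablets supplied at the site. The protocol does not say the dose is taken elsewhere.
- *Section 5.7 makes the product document binding on enrollment.* The entry there, "Single drug covered by prescribing information: Azithromycin E.U. Summary of Product Characteristics", serves to judge expectedness for expedited reporting.

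**Conclusion.** The point holds as a mismatch between the entry rule and the contraindication the protocol reports. For a Cohort A candidate allergic to another macrolide, exclusion is available and, once the undue-risk criterion is considered met, mandatory and non-waivable. Whether it is met is left to the investigator.

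Severity is minor to should-fix: minor if rated on demonstrated consequence, should-fix if weighed by the safety subject and the small cost of repair. A reader might infer that contraindicated patients will be enrolled and dosed. The documents do not show that even one would be.

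The conclusion assumes that 5.1.2.9 reports the contraindication correctly, since the product document was not available for this review. It uses no assumed prevalence or reaction rate.

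**What to change.** In the synopsis and in Section 4.1.2, keep the allergy criterion and add the words *or any other macrolide antibiotic* after azithromycin. The extension may be limited to Cohort A, as the hearing-impairment exclusion already is, because Cohort B receives no azithromycin. Apply it from the medication-allergy history collected under 4.5.2.

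The cost is one line in each of two places, which can go into the next amendment, with no new assessment. A few candidates may become ineligible, including any who are allergic to another macrolide but have tolerated azithromycin. If the sponsor wants to keep those patients eligible, the criterion should say so and give the reason.

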4.2 METHOD OF TREATMENT ASSIGNMENT AND BLINDING

Patients will be randomized to the treatment arms through the interactive voice/web-based response system (IxRS). After written informed consent has been obtained, patients in Cohort A will be randomized in a 1:1 ratio to one of two open-label treatment arms (azithromycin, 250 mg/QD plus daily SOC medications or daily SOC medications). Patients in Cohort B will continue to receive daily SOC medications.

Permuted block randomization will be performed centrally for Cohort A and stratified by region (United States or United Kingdom/Canada) and prior exacerbation history (2, ≥ 3). During the open-label treatment period, the IxRS will make study treatment kit assignments.

In Cohort A, the number of COPD patients with chronic bronchitis (COPD-CB) will be capped at ≤ 65 .

4.3 STUDY INTERVENTIONS AND TREATMENTS RELEVANT TO THE STUDY DESIGN

The IMPs for this study are azithromycin and HP ^{129}Xe . All patients will continue their COPD therapy as recommended in published COPD guidelines (GOLD 2019) or BTS guidelines (NICE 2018). Required COPD inhaler therapies, consisting of LABA and/or LAMA with or without ICS therapy, are considered non-IMPs for this study.

4.3.1 Study Treatment Formulation and Packaging

4.3.1.1 **Azithromycin**

Azithromycin will be supplied by the Sponsor in the approved 250-mg tablet dosage form. For information on the azithromycin formulation, see the Summary of Product Characteristics for azithromycin.

4.3.1.2 **Hyperpolarized ^{129}Xe**

^{129}Xe is created by passing a gas mixture of xenon, helium, and nitrogen through the Hyperpolarizer. The gas mixture will be provided by the clinical site and will be hyperpolarized at the clinical site. For information on the gas mixture, see the study imaging manual.

4.3.2 Study Treatment Dosage, Administration, and Compliance

The treatment regimens are summarized in Section 3.1. Details on treatment administration (e.g., dose and timing) should be noted on the Study Drug Administration electronic Case Report Form (eCRF). Guidelines for treatment interruption or

discontinuation for patients who experience adverse events are provided in Section 5.1.3.

4.3.2.1 Azithromycin

Patients in Cohort A randomized to treatment intervention will receive generic azithromycin 250 mg taken orally (PO) QD. Patients will receive a 3-month supply of azithromycin 250-mg tablets at Visit 2 (baseline), Visit 4 (Week 12), Visit 5 (Week 24), and Visit 6 (Week 36) at the study site. Patients randomized to receive azithromycin will receive a maximum of 336 doses with a tablet strength of 250 mg. All patients will be provided with a diary to track daily study treatment and the date of any AEx events.

4.3.2.2 Hyperpolarized ^{129}Xe

HP xenon (^{129}Xe) will be administered at *specified timepoints and the total dose bag volume should target 20% of the patient's forced vital capacity* followed by a breath hold of up to 15 seconds. Subsequent ^{129}Xe doses will only be administered once the patient is ready to proceed. Patients will be monitored by a qualified medical professional for the duration of the xenon dose and post-procedural period, as well as the MRI. *Refer to the study imaging manual for details.*

HP ^{129}Xe MRI scans will be acquired according to procedures described in the study imaging manual. Scans will be centrally processed and analyzed per the Independent Review Charter (IRC). ^{129}Xe MRI scans will be made available to each participating clinical site when the study has been completed and database has been locked. The study imaging manual and IRC are provided to ensure image acquisition and processing is standardized across all clinical sites.

